4.4. Replacement of Patients

A patient who is enrolled but does not complete the treatment period will not be replaced.

4.5. Rescreening

A patient who is screened and does not meet study inclusion and exclusion criteria will not be considered for screening again.

4.6. Screening Failure

Screening failures are defined as participants who consent to participate in the clinical study but are not subsequently randomized/enrolled in the study. Minimal information includes but is not limited to demography, screening failure details, eligibility criteria, and any adverse events or serious adverse events.

5. TREATMENTS

5.1. Investigational Medicinal Products Used in the Study

IMP is defined as the test IMP and placebo IMP. Details of the test and placebo IMPs are presented in [Table 6](#).

Table 6: Investigational Medicinal Products Used in the Study

IMP name	Test IMP	Placebo IMP
Trade name and INN, if applicable, or company-assigned number	Fremanezumab (formerly LBR-101, PF-04427429, or RN 307)	n/a
Formulation	Solution for injection	Solution for injection
Unit dose strength(s) dosage level(s)	225 mg/1.5 mL 675 mg sc quarterly, 225 mg sc monthly, or 675 mg sc loading dose followed by 225 mg monthly	n/a
Route of administration	Fremanezumab will be administered as sc injections (1.5 mL per injection) by qualified study personnel at the investigational center.	Placebo will be administered as sc injections (1.5 mL per injection) by qualified study personnel at the investigational center.
Packaging	Fremanezumab will be provided in prefilled syringes contained in uniquely numbered kits and stored (refrigerated at 2°C to 8°C) at the investigational centers. Prefilled syringes (1.5 mL) will contain fremanezumab at a concentration of 150 mg/mL.	Placebo will be provided in prefilled syringes contained in uniquely numbered kits and stored (refrigerated at 2°C to 8°C) at the investigational centers. Prefilled syringes (1.5 mL) will contain the same vehicle and excipients as those for active infusion and injection.
Manufacturer	Teva Branded Pharmaceutical Products R&D, Inc. [REDACTED] [REDACTED]	Teva Branded Pharmaceutical Products R&D, Inc. [REDACTED] [REDACTED]

IMP=investigational medicinal product; INN= International Nonproprietary Names; n/a=not applicable; sc=subcutaneous.

The recommended sc injection sites follow the National Institutes of Health Patient Education Guidelines of September 2015, which are available in [Appendix U](#) of this document and at the following website: http://www.cc.nih.gov/ccc/patient_education/pepubs/subq.pdf. The suggested sites of injection are back of upper arms, lower abdomen/belly/waistline, and front of thighs. At each visit, the injections should be given in a different location (eg, not in precisely the same place), and study staff member(s) responsible for administration of injections should inspect previous injection sites to ensure that they are free of bruising and tenderness and that proper rotation of sites is performed. The total number of sc injections and their locations will be recorded for each dosing visit (visits 1 through 10). A 1.5-mL volume from each prefilled syringe must be injected sc for dosing to be considered complete.

5.1.1. Test Investigational Medicinal Product

Fremanezumab is a fully humanized IgG2a/kappa monoclonal antibody derived from a murine precursor. Additional details may be found in [Table 6](#) and in the IB for fremanezumab.

5.1.1.1. Starting Dose and Dose Levels

Patients rolling over from Study TV48125-CNS-30056 with ECH:

- Patients who were in the fremanezumab 900-mg iv loading dose group will receive fremanezumab at 225 mg sc as a single injection at visit 1 and every 4 weeks thereafter through week 36 (visit 10). For blinding, these patients will also receive 2 placebo sc injections at visits 1, 4, 7, and 10.
- Patients who were in the placebo group and the fremanezumab 675-mg sc quarterly group will receive fremanezumab at 675 mg sc as 3 injections (225 mg/1.5 mL) at visit 1 and every 12 weeks thereafter through week 36 (visit 10). For blinding, patients will receive 1 single placebo sc injections at visits 2, 3, 5, 6, 8, and 9.

After 15 June 2018, only patients who participated in the ECH study (Study TV48125-CNS-30056) will be enrolled for active treatment. Patients with CCH will be rolled over from Study TV48125-CNS-30057 until 15 June 2018 as follows (after 15 June 2018 no additional CCH patients will be enrolled):

- Patients who were in the fremanezumab 900-mg iv loading dose group and the fremanezumab 675-mg sc loading dose group will receive fremanezumab at 225 mg as a single sc injection (225 mg/1.5 mL) at visit 1 and every 4 weeks thereafter through week 36 (visit 10). For blinding, these patients will also receive 2 sc placebo injections at visit 1.
- Patients who were in the placebo group will receive a loading dose of fremanezumab at 675 mg as 3 sc injections (225 mg/1.5 mL) at visit 1 and fremanezumab at 225 mg administered as a single sc injection every 4 weeks thereafter through week 36 (visit 10).

After 15 June 2018, only patients who participated in

the ECH study (Study TV48125-CNS-30056) will be enrolled for active treatment. All CCH patients included in this study have been asked to discontinue treatment and are encouraged to continue in the ADA and safety follow-up portion of this study. At the time of unblinding the treatment code in Study TV48125-CNS-30057 (planned for Q4 2018), those CCH patients who were receiving placebo in Study TV48125-CNS-30057 (ie, never received any study drug) will not be required to complete additional safety follow-up visits, and will be discharged from the study.

Of note, blinding of the pivotal studies and the initial treatments during this long-term safety extension study will be maintained throughout study participation.

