All patients will return to the study center approximately every 4 weeks after administration of the first dose of the IMP (visit 1 [week 0]) through the end-of-treatment (EOT) visit (visit 11 [week 40]), which will occur approximately 4 weeks after administration of the last dose of the IMP (week 36). Patients will return for a follow-up visit (visit 12) to evaluate ADAs, biomarkers, and safety (adverse events and concomitant medications) approximately 7.5 months after the last dose of the IMP. Patients who withdraw from the study before completing the 40-week treatment period will have EOT visit procedures and assessments performed on the last day the patients received the IMP or as soon as possible thereafter, and they will be asked to return for a follow-up visit approximately 7.5 months after their last dose of the IMP.

Patients who enter the long-term safety follow-up study for safety follow-up only will not follow the same visit schedule as that for patients receiving treatment. The procedures and assessments for the patients participating in the safety follow-up are described in [Table 5](#).

CH attack information will be captured daily throughout the treatment period (ie, visit 1 [week 0] through visit 11 [week 40]) using an electronic diary device. Assessments of change in quality of life, satisfaction with treatment, and health status (using the Hospital Anxiety and Depression Scale, EuroQol-5 Dimension questionnaire, 12-Item Short-Form Health Survey, Impact on Partner and Family questionnaire, and Work Productivity and Activity Impairment questionnaire); satisfaction with treatment (using the Patient Perceived Satisfactory Improvement and Patient Global Impression of Change scale); safety evaluations; blood collection for pharmacokinetic, immunogenicity, and biomarker analyses; and urine sampling for biomarker analysis will be performed at pre-specified time points.

The long-term safety of fremanezumab in patients with CH will be evaluated through adverse event and concomitant medication inquiries, ECGs, vital signs measurements, clinical laboratory tests, physical examinations, injection site assessments, assessments for anaphylaxis and hypersensitivity, and administration of the eC-SSRS.

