Study TV48125-CNS-30057 (CCH) Prior to 15 June 2018 termination of CCH Study TV48125-CNS-30057. No additional CCH patients will be enrolled after 15 June 2018 for active treatment.	Fremanezumab 900-mg iv loading dose group ^c	Fremanezumab at 225 mg sc monthly (approximately every 4 weeks) through week 36
	Fremanezumab 675-mg sc loading dose group ^f	Fremanezumab at 225 mg sc monthly (approximately every 4 weeks) through week 36
	Placebo group ^e	Fremanezumab 675-mg sc loading dose followed by monthly (approximately every 4 weeks) fremanezumab at 225 mg sc through week 36

^a In order to maintain blinding throughout the study, the number of sc injections at each visit will be the same for all patients rolling over from Study TV48125-CNS-30056, regardless of their assigned treatment group. Thus, patients will receive 3 sc injections of test IMP (1.5-mL injections each containing fremanezumab at a concentration of 150 mg/mL) or 1 sc injection of test IMP (1.5-mL injection containing fremanezumab at a concentration of 150 mg/mL) and 2 sc injections of placebo IMP (1.5-mL injections) at visits 1, 4, 7, and 10, and a single sc injection of test IMP or placebo IMP at visits 2, 3, 5, 6, 8, and 9.

^b In order to maintain blinding throughout the study, the number of sc injections at each visit will be the same for all patients rolling over from Study TV48125-CNS-30057, regardless of their assigned treatment group. Thus, patients will receive 3 sc injections of either test IMP (1.5-mL injections each containing fremanezumab at a concentration of 150 mg/mL) or 1 sc injection of test IMP (1.5-mL injection containing fremanezumab at a concentration of 150 mg/mL) and 2 sc injections of placebo IMP (1.5-mL injections) at visit 1, and patients will receive a single sc injection of test IMP (1.5-mL injection containing fremanezumab at a concentration of 150 mg/mL) at all other visits.

^c Fremanezumab at 900 mg iv at visit 2 (week 0) of the pivotal study and fremanezumab at 225 mg sc at visits 3 and 4 (weeks 4 and 8, respectively) of the pivotal study.

^d Fremanezumab at 675 mg sc at visit 2 (week 0) of the pivotal study and placebo sc at visits 3 and 4 (weeks 4 and 8, respectively) of the pivotal study.

^e Placebo iv and sc at visit 2 (week 0) of the pivotal study and placebo sc at visits 3 and 4 (weeks 4 and 8, respectively) of the pivotal study.

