All patients will return to the investigational center approximately every 4 weeks after administration of the first dose of the IMP (visit 1 [week 0]) through the end-of-treatment (EOT) visit (visit 11 [week 40]), which will occur approximately 4 weeks after administration of the last dose of the IMP (week 36). Patients will return for a follow-up visit (visit 12) to evaluate ADAs, biomarkers, and safety (adverse events and concomitant medications) approximately 7.5 months after the last dose of the IMP. Patients who withdraw from the study before completing the 40-week treatment period will have EOT visit procedures and assessments performed on the last day the patients received the IMP or as soon as possible thereafter, and they will be asked to return for a follow-up visit approximately 7.5 weeks after their last dose of IMP.

Patients who enter the long-term safety follow-up study for safety follow-up only will not follow the same visit schedule as that for patients receiving treatment. The procedures and assessments for the patients participating in the safety follow-up are described in Table 5.

CH attack information will be captured daily throughout the treatment period (ie, visit 1 [week 0] through visit 11 [week 40]) using an electronic diary device. Assessments of change in quality of life and health status (using the Hospital Anxiety and Depression Scale [HADS], EuroQol-5 Dimension [EQ-5D] questionnaire, 12-Item Short-Form Health Survey [SF-12], Impact on Partner and Family questionnaire, and Work Productivity and Activity Impairment [WPAI] questionnaire); satisfaction with treatment (using the Patient-Perceived Satisfactory Improvement [PPSI] and the Patient Global Impression of Change [PGIC] scale); safety evaluations; blood collection for pharmacokinetic, immunogenicity, and biomarker analyses; and urine sampling for biomarker analysis will be performed at pre-specified time points (Table 4).

[figure not shown]
The long-term safety of fremanezumab in patients with CH will be evaluated through adverse event and concomitant medication inquiries, ECGs, vital signs measurements, clinical laboratory tests, physical examinations, injection site assessments, assessments for anaphylaxis and hypersensitivity, and administration of the electronic Columbia-Suicide Severity Rating Scale (eC-SSRS).

The end of study is defined as the date the last patient attends the follow-up visit.

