Return electronic diary device											X	
Blood sample for pharmacokinetics analysis ^f		X	X	X	X	X	X	X	X	X	X	
Blood sample for serum ADA analysis ^s				X			X			X	X	X
Blood collection for serum, plasma, and RNA biomarker analysis ^t				X			X			X	X	X
Urine collection for biomarker analysis				X			X			X	X	X
HADS ^p		X					X			X	X	
EQ-5D questionnaire ^p		X					X			X	X	
SF-12 ^p		X					X			X	X	
WPAI questionnaire ^p		X		X			X			X	X	
Impact on Partners and Family questionnaire ^{p,u}		X		X			X			X	X	
PPSI ^v		X	X	X			X			X	X	
PGIC scale ^v		X	X	X			X			X	X	
Wearable sensor substudy data capture ^w	X										X	

Table 4: Study Procedures and Assessments for Treated Patients (Continued)

	Double-blind treatment period ^a											Follow-up period
Visit number	V1 ^b	V2	V3	V4	V5	V6	V7	V8	V9	V10	V11	V12
Procedures and assessments (completed before dosing, when applicable, unless otherwise noted)	Week 0 (day 0)	Week 4 (±3 days)	Week 8 (±3 days)	Week 12 (±3 days)	Week 16 (±3 days)	Week 20 (±3 days)	Week 24 (±3 days)	Week 28 (±3 days)	Week 32 (±3 days)	Week 36 (±3 days)	EOT/early withdrawal week 40 (±3 days)	Follow-up week 68 (±1 week) ^c
Wearable sensor check and compliance check		X	X	X	X	X	X	X	X	X	X	
Return wearable sensor											X	
Study IMP administration ^x	X	X	X	X	X	X	X	X	X	X		
Injection site reaction/pain assessment ^y	X	X	X	X	X	X	X	X	X	X		
Anaphylaxis and hypersensitivity reaction assessment ^z	X	X	X	X	X	X	X	X	X	X		

^a An unscheduled visit may be performed at any time during the study at the patient’s request and as deemed necessary by the investigator. The date and reason for the unscheduled visit will be recorded on the CRF as well as any other data obtained from procedures and assessments.

^b Visit 1 of the current study corresponds with the EOT visit (visit 5) of the pivotal efficacy studies. EOT visit procedures/assessments must be completed before the patient begins participation in this study, and the EOT procedures/assessments will not be repeated at visit 1 of this study. The EOT visit procedures/assessments are detailed in the protocols for Studies TV48125-CNS-30056 and TV48125-CNS-30057.

^c For patients who discontinue the study early and patients who achieve CH remission (ie, meaning they stop and may restart treatment depending upon whether or not CH attacks recur), the follow-up visit will be approximately 7.5 months after the last dose of IMP.

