9.1. Sample Size and Power Considerations

There are no statistical considerations for the sample size. Up to 600 patients from the Phase 3 pivotal efficacy studies (Studies TV48125-CNS-30056 and TV48125-CNS-30057) are expected to enroll in this study

The sample size for each of the pivotal studies TV48125-CNS-30056 for ECH and TV48125-CNS-30057 for CCH is 300 patients. All of the 600 patients participating in the pivotal studies will roll over to the long-term safety study. Approximately 360 patients (out of the completers from the pivotal studies) will be offered to receive treatment during 40 weeks, and these patients will return for a follow-up visit approximately 7.5 months after the last dose of the IMP. Approximately 240 patients (including early termination patients in the pivotal studies) will be offered to continue in a long-term safety evaluation collecting AEs, SAEs, and for ADA evaluation approximately 7.5 months after administration of the last dose of the IMP.

Prior to 15 June 2018, patients from the ECH study and the CCH study were enrolled. After 15 June 2018, only patients who participated in the ECH study (Study TV48125-CNS-30056) will be enrolled for active treatment. At the time of unblinding the treatment code in Study TV48125-CNS-30057 (planned for Q4 2018), those CCH patients who were receiving placebo in Study TV48125-CNS-30057 (ie, never received any study drug) will not be required to complete additional safety follow-up visits, and will be discharged from the study.

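### The CCH discharge rule selects by pivotal-study placebo arm and calls those patients unexposed, although some were dosed with fremanezumab in this study

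*Protocol*

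**What the plan says.** The discharge rule appears nine times in the protocol: three times in the synopsis, and in Sections 1.1.3, 3.1, Figure 1 footnote a, 5.1.1.1, 7.8 and 9.1. In Section 5.1.1.1 it reads: "CCH patients who were receiving placebo in Study TV48125-CNS-30057 (ie, never received any study drug) will not be required to complete additional safety follow-up". Section 9.1 completes the sentence: they "will not be required to complete additional safety follow-up visits, and will be discharged from the study". The trigger is the unblinding of 30057, planned for Q4 2018.

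The same Section 5.1.1.1 sets the treatment of CCH patients rolling over from 30057: "Patients who were in the placebo group will receive a loading dose of fremanezumab at 675 mg as 3 sc injections" at visit 1, then 225 mg every 4 weeks through week 36. Table 3 and Section 5.3.1 agree. SAP Sections 5.1 and 8.2 make these patients a treatment group of their own.

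For treated patients, Section 9.1 says "these patients will return for a follow-up visit approximately 7.5 months after the last dose of the IMP". For patients who stop early, Table 4 footnote c says "the follow-up visit will be approximately 7.5 months after the last dose of IMP", and the synopsis says "they will be asked to return for a follow-up visit approximately 7.5 months after their last dose of the IMP". Appendix B gives the same interval. The matching sentence in Section 3.1 differs in its unit: "they will be asked to return for a follow-up visit approximately 7.5 weeks after their last dose of IMP".

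**The concern.** The rule picks patients by their arm in 30057 and uses *ie* to equate that arm with never having been exposed. This is right for placebo patients who entered 30058 only for antidrug-antibody (ADA) and safety follow-up. It is wrong for those who rolled over for treatment. For them the selector contradicts its own parenthetical and the 7.5-month return rule, and Section 9.1 contains both rules.

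If a site acts on the selector, the visit-12 ADA sample and the active late safety inquiry are lost for exposed patients. After a patient's study period, serious events and events of special interest reach the sponsor only if the investigator happens to learn of them (Sections 7.1.2 and 7.1.5). Pregnancies remain reportable for at least 7.5 months after IMP (Section 7.2). The loss would fall on one SAP treatment group, the 675-mg load followed by 225 mg monthly, which contains only 30057 placebo patients. The primary objective is long-term safety, and Section 2.1 commits to evaluating CCH data against all objectives.

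**Working it through.** **Does the rule reach dosed patients?**

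- In Section 5.1.1.1 it directly follows the statement that all CCH patients in the study were asked to stop treatment, a group that includes dosed patients.
- None of the nine instances mentions exposure in 30058 or limits discharge to follow-up-only patients.
- A 30057 placebo patient treated here has received between 675 mg (visit 1 only) and 675 + 9 × 225 = 2,700 mg (all ten doses).

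**When is visit 12 due?** Table 4 puts the last dose at week 36 and visit 12 at week 68 ± 1 week.

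- Interval: 68 − 36 = 32 weeks = 224 days (217 to 231).
- The documents give Q4 2018 and no exact date, so both ends of the quarter are used.

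| Unblinding date | Visit 12 still outstanding if last dose was after | Range with ± 7 days |
|---|---|---|
| 1 Oct 2018 | 1 Oct − 224 d = 19 Feb 2018 | 12 to 26 Feb |
| 31 Dec 2018 | 31 Dec − 224 d = 21 May 2018 | 14 to 28 May |

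**Latest possible dose.** CCH treatment was stopped as of 15 June 2018, so the last possible dosing day is taken as 14 June. Visit 12 is then due on 14 Jun 2018 + 224 d = 24 Jan 2019 (17 to 31 Jan), after all of Q4.

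| Discharge | Follow-up achieved | Share of 224 d | Half-lives at 36.2 to 32.2 d (Section 1.2.2.1) | Half-lives at 44.8 d |
|---|---|---|---|---|
| 1 Oct 2018 | 109 d | 48.7% | 109/36.2 = 3.0 to 109/32.2 = 3.4 | 109/44.8 = 2.4 |
| 31 Dec 2018 | 200 d | 89.3% | 200/36.2 = 5.5 to 200/32.2 = 6.2 | 200/44.8 = 4.5 |

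The last column uses the protocol's own equation of 7.5 months with 5 half-lives (Section 5.4.2): 224/5 = 44.8 days each.

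**Sensitivity to the interval.**

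- Reading 7.5 months as 7.5 × 30.4375 = 228 days moves the cut-offs by 4 days, to 15 Feb and 17 May 2018.
- On the 7.5-week figure in Section 3.1 (52.5 days), visit 12 after a 14 June dose would be due on 5 or 6 August 2018, and nothing would be lost. The synopsis, Table 4 footnote c and Appendix B all say months for early stoppers, so months is used here.

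**The case against.** The best reply is that this is a missing qualifier and no one decided to drop exposed patients. The parenthetical carries the real criterion, and a patient given 675 mg in 30058 plainly does not meet it. The code break in 30057 is needed to learn exposure only for CCH patients who were not dosed here, which supports that reading. Under it, the two rules in Section 9.1 do not collide. A site would also have to label as unexposed someone it had injected itself: Table 3 footnote b says that, after visit 1, "patients will receive a single sc injection of test IMP (1.5-mL injection containing fremanezumab at a concentration of 150 mg/mL) at all other visits", and visit 1 includes active drug too.

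As an account of intent this is probably right, and it makes misapplication less likely. It does not settle the text. *Ie* states an equivalence and adds no condition, the item revealed at unblinding is the 30057 arm, and the protocol gives no rule for cases where arm and exposure disagree.

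Other limits stand:

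- The 14 June dose is the extreme case. For an assumed 31 May dose, follow-up is 123 to 214 days (55% to 96% of 224).
- At the Section 1.2.2.1 half-life, five half-lives after 14 June are 161 to 181 days, reached between 22 November and 12 December 2018.
- ADA samples at visits 4, 7, 10 and end of treatment remain for patients who reached them, as do adverse events up to discharge.
- Attendance by CCH patients after 15 June 2018 was encouraged, not compulsory, so some visit-12 data would be missing anyway.
- The ADA impact analysis is outside this SAP (Section 13).
- Nothing in the documents shows that an exposed patient was in fact discharged.

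**Conclusion.** The concern holds. As written, the rule discharges 30057 placebo patients who received fremanezumab in 30058 and describes them wrongly. The potential loss is material if unblinding comes early in Q4 2018 (about half of the planned follow-up for a 14 June dose) and small if it comes at the end of the quarter (about 11% lost: 100% − 89.3%).

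This rests on a 7.5-month interval taken as 224 days, unblinding within Q4 2018, and a site following the arm label. The number of patients affected cannot be derived from the documents. No inferential analysis is affected, because SAP Section 7 plans none. It should be fixed because it bears on the safety follow-up of exposed patients and the correction is small.

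**What to change.** Restrict discharge to CCH patients who received placebo in 30057 and no fremanezumab in 30058, in all nine places. Before the unblinding, send sites a clarification letter stating that CCH patients dosed in 30058 keep visit 12, and carry the wording into the next amendment. Sites can identify these patients from their own dosing records, since every CCH dosing visit includes active drug.

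The cost is one letter plus amendment text, which may need ethics and authority approval (Appendix C). No visits or samples are added.

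The letter is useful only before the unblinding. SAP Section 2.1 records study completion in Q2/2019. At that stage the remaining, optional step is a disposition row under SAP Section 5.2 for patients discharged at the 30057 unblinding, split by whether they received fremanezumab in 30058. This would show how the rule was applied.
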